Clinical Trial Protocol

TITLE: Prospective, Multicenter, Randomized, Single-blind, Parallel-controlled Clinical Trial Protocol for the Safety and Efficacy of Clinical Applications of the Endoscopic Instrument Control System

PROTOCOL ID: SDWG-NST600S-CT

DOCUMENT TYPE: Study protocol

DATE: 2019-09-01

SPONSOR: The Third Xiangya Hospital of Central South University

COLLABORATOR: The Affiliated Hospital of Qingdao University

Study protocol

1. Study purpose

To evaluate the safety and efficacy of the MicroHand S endoscopic instrument control system by using it in clinical treatment for the participants. Statistical analysis is conducted to determine whether the efficacy of the test product is non-inferior to that of the control product and to observe the incidence of organ and vascular injury related to the test product. Thus, to verify the safety and efficacy of the MicroHand S endoscopic instrument control system developed by WEGO Surgical Robot Co., Ltd in clinical application.

2. Content

This clinical trial is a prospective, multicenter, randomized, single-blind, parallel-controlled study. The instrument used in the experimental group is the endoscopic surgical robotic system developed by WEGO Surgical Robot Co., Ltd., and the instrument used in the control group is the endoscopic surgical robotic system developed by Intuitive Surgical.

Before patients are enrolled in this clinical study, the researchers will do a detailed screening of the subjects based on the inclusion and exclusion criteria to determine if the patients are appropriate for the clinical study. Patients who meet the conditions of the study will be required to sign an informed consent form. Then they will be randomly assigned to the test group or the control group. The surgical robot system will be used for treatment in both groups to evaluate the primary and secondary outcome measures and to observe the incidence of organ and vascular injury.

Finally, we evaluate the safety and efficacy of the test product through the comparison of the data obtained from the test group and the control group during the treatment.

3. Background

The development direction of medical treatment in the 21st century is to preserve the physiological structure and function of patients as much as possible. Compared with conventional laparotomy, minimally invasive surgery has obvious advantages in terms of treatment effect, pain relief, recovery, and medical cost. The endoscopic instrument control system, also known as the surgical robot, is a breakthrough in the field of surgery, which greatly expands the indications of minimally invasive surgery.

The endoscopic instrument control system has the characteristics of minimally invasive surgery and more technical advantages:

- (1). It can accurately simulate the movements of human hands, wrists and fingers with multi-degree of freedom.
- (2). It can proportionally reduce the surgeon's range of motion and improve the accuracy of surgical procedures.
- (3).The tremor filtering system filters the hand vibration of the surgeon and improves the

stability of the operation.

(4).The imaging system provides the surgeons with a three-dimensional magnifying view (5 to 10 times) of the field image to enhance the surgeon's visual perception.

(5). Using a surgical robot, the surgeon can sit in a comfortable chair so that they can relieve the operator's fatigue, reduce the probability of making mistakes due to tiredness, and improve the safety of the operation.

(6). The surgeons can use the "high-speed broadband" technology to interface with other digital devices and to control the surgical robot for a surgery.

From 2000 to the present, the "Da Vinci" robotic system has become the most commonly used robotic surgical system because of its superior design and performance. Since its inception, the system has been used in a variety of operations including cardiac surgery, general surgery, gynecology, head and neck surgery, thoracic surgery and urology.

As of October 2018, more than 4,000 systems were in use worldwide, with more than 5 million patients benefiting from the advanced minimally invasive techniques of da Vinci surgical robot. But its high cost, expensive annual maintenance cost, and accessory instruments limit the use of da Vinci's surgical systems in developing countries like China.

The endoscopic surgical robotic system developed by WEGO Surgical Robot Co., Ltd. is a minimally invasive surgical robotic system independently developed by China which is the first successful minimally invasive surgical robotic system in China with property rights. It can complete complex suture and knotting, replace the traditional planar imaging system with a three-dimensional stereo vision system to make the surgical field clearer. The adjustable mapping ratio and more practical energy device are its unique specialty. It can also greatly reduce the cost of robotic surgery.

The test product has passed the test of Beijing Medical Device Quality Supervision and Inspection Center of the China Food and Drug Administration. All met the standard requirements and issued qualified registration inspection. The clinical verification will be performed by the Third Xiangya Hospital of Central South University and the affiliated hospital of Qingdao University, to prove the safety and efficacy of this product.

4. Precautions of the test product

1. Please read the user manual and instructions carefully before using the console.
2. Operators are required to have certain qualifications. They are required for more than 5 years of experience in laparoscopic surgery, more than 1 year of experience in robotic surgery, and having been trained to operate the test product skillfully.
3. Before each operation, you must check whether the console is damaged, whether the control panel displays normal, and whether the connecting wires and interfaces are integrated.
4. After turning on the power, you shouldn't operate until the console completely starts and the operative arms and other surgical preparations are prepared.
5. The operation should be meticulous and gentle, avoiding excessive and violent movements to cause damage to subjects or instruments.
6. Emergency preparation for accidents must be done before surgery.
7. Disconnection is prohibited during the operation.
8. Do not embed any foreign components. Any foreign components embedded can cause

permanent damage to the product. If it does, immediately turn off the power and contact a qualified service person for repairing.

9. Do not attempt to disassemble or modify the product.

10. The console should be placed in a clean, dry, suitable temperature and humidity environment, having regular inspection and maintenance.

11. If the console has any malfunction, stop the procedure and report it to the manufacturer in time.

5. Study Methods

- (1) This study uses a multicenter, randomized, single-blind, parallel-controlled method to observe the efficacy and safety of the MicroHand S endoscopic instrument control system in clinical application.
- (2) The subjects' vital signs are recorded before the start of this study, which include blood routine, liver and kidney function, electrolytes, coagulation function, electrocardiogram, urine/blood pregnancy test (female) and related imaging examination. Preoperative combined medications are also recorded.
- (3) Qualified subjects are divided into the experimental group and the control group by randomized number given in an envelope. Both the endoscopic instrument control systems in two groups are examined before the test. After anesthesia, the endoscopic instrument control system is placed in an appropriate position. Then we connect the wires and power up the system. According to the requirements of the surgery, the operative arms are placed and slowly pushed through the Trocars of the abdominal wall. The surgeons start to perform the operation.
- (4) Surgical success rate, intraoperative blood loss, operative time, and installation time are recorded, as well as whether adjacent organs and blood vessels are injured due to the malfunction of the test system. The breakage rate of gallbladders is calculated. Surgeons need to fill the satisfaction questionnaire after the surgery.
- (5) Subjects take a test in 24 ± 2 hours after surgery using visual analogue scale (VAS) to evaluate the pain score. Postoperative blood routine examination, liver and kidney function, and electrolyte examination are performed. Time to first flatus, postoperative complications and hospital stay are recorded. Postoperative combined medications are also recorded. Adverse events and severe adverse events are assessed separately in 30 ± 5 days after surgery.
- (6) After the follow-ups of all subjects, the data will be arranged for statistical analysis. Ultimately the data of the two groups will be compared, so as to prove whether the experimental product developed by WEGO Surgical Robot Co., Ltd is non-inferior to the control group.

6. Arms and Interventions

- (1) Experimental group: MicroHand S endoscopic instrument control system
Using the MicroHand S endoscopic instrument control system to treat gallstone or cholecystitis in minimal invasive surgery.

(2) Control group: da Vinci endoscopic instrument control system
Using the da Vinci endoscopic instrument control system to treat gallstone or cholecystitis in minimal invasive surgery.

7. Subject recruitment

7.1 Inclusion criteria

- (1) 18-65 years old, male or female
- (2) American Society of Anesthesiologists (ASA) Level 1, Level 2 or Level 3
- (3) BMI 18-30Kg/m²
- (4) Benign gallbladder diseases such as acute or chronic cholecystitis, gallstones and polypoid lesions of gallbladder
- (5) Subjects or their legal representatives/guardians voluntarily participate in clinical trials and have signed informed consent

7.2 Exclusion criteria

- (1) Participating in any other clinical trial within 30 days before signing the informed consent form
- (2) Pregnancy or lactation
- (3) With a history of epilepsy or psychosis
- (4) With a history of previous operations at related sites
- (5) Severe cardiovascular and cerebrovascular diseases with New York grade III-IV cardiac function or pulmonary insufficiency that can't tolerate the operation
- (6) Severe liver and kidney insufficiency such as cirrhosis and renal failure
- (7) Acute cholecystitis lasting for more than 72 hours, acute cholecystitis with severe complications such as cholecystitis, gangrene, perforation, etc., and gallbladder thickness thicker than 10 mm
- (8) Acute cholangitis, gallstone with acute pancreatitis, primary common bile duct stones, intrahepatic bile duct stones and obstructive jaundice
- (9) Gallbladder cancer or protuberant lesions are suspected to be cancerous
- (10) Severe allergic constitution and suspected or identified addicts to alcohol or drugs
- (11) Abdominal infection, peritonitis, diaphragmatic hernia, severe systemic infection or metastatic diseases
- (12) Other situations that researchers consider it inappropriate to participate in this clinical trial

7.3 Inclusion time

After signing the informed consent, subjects who meet the inclusion criteria and do not meet the exclusion criteria can be enrolled within 14 days. It is expected to take 12 months from the first case to the last case.

7.4 The expected duration of the study

The expected duration time of each subject is 33 days. Considering that the robotic

surgery has not been widely carried out in China, as well as the poor subject compliance, the overall duration of this clinical trial is expected to be 13 months.

7.5 The expected duration time of each subject

Each subject is observed up to 30 days after surgery, and efficacy and safety are evaluated at the end of the follow-up. So the expected duration of each subjects is 33 days. The additional 3 days are used for preoperative examination.

7.6 Number of subjects required

In this clinical trial, 168 patients are enrolled, including 84 in the experimental group and 84 in the control group.

7.7 Drop-outs and removal of the subjects

All subjects who sign the informed consent form and participate in the study, whenever they withdraw from the study for any reason, as long as they do not complete the observation period specified in the protocol, they are shedding cases. Usually in these situations:

- (1) The subject or his/her legal guardian requests to withdraw from the clinical trial.
- (2) Adverse events (AE), severe adverse events (SAE), or any device defects that prevent subjects from continuing to participate in the study.
- (3) The researchers consider it medically necessary for the subjects to terminate the study.
- (4) Other reasons for subjects to suspend the study.

When the subject drops out, the researcher should take various methods, such as paying a visit, making a follow-up appointment, phone call, letter, etc., to contact the subject as far as possible and ask the reason. Any drop-out due to adverse events should be recorded in the CRF form and notified to the sponsor, regardless of whether there is a causal relationship with the test product or not. All subjects enrolled in the study should retain various original data and documents, both for retention and for intentional analysis (ITT Analysis).

All subjects meeting the following criteria should be removed:

- (1) Those found to violate the inclusion criteria or meet the exclusion criteria during the trial.
- (2) Withdrawing the informed consent.
- (3) The informed consent form is not signed or there is no informed consent process.
- (4) Failing to obtain observation data.

Case removal is one of the key indicators to determine the endpoint data set of clinical trials. If there is a condition that affects the treatment or safety evaluation of the case, such as unavailable observational data, the case should be considered as not included in the analysis set. It must be decided after discussion between the principal investigator, the data manager, the statistical analyst and the sponsor.

8. Efficacy evaluation

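### Section 7.7 lets an adverse event or device defect end a subject's observation after the single operation, without requiring the 30-day safety assessment

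*Protocol*

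**What the plan says.** Protocol section 7.7 defines drop-out by incomplete observation: whatever the reason for leaving, "as long as they do not complete the observation period specified in the protocol, they are shedding cases". Ground (2) in its list of usual situations is "Adverse events (AE), severe adverse events (SAE), or any device defects that prevent subjects from continuing to participate in the study". Ground (3) is an investigator's judgement that ending the study is medically necessary.

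After a drop-out, section 7.7 requires three things:

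- The site tries several routes (visit, follow-up appointment, telephone, letter) "to contact the subject as far as possible and ask the reason".
- The site enters an AE-related drop-out in the CRF and reports it to the sponsor, whatever the causal relationship.
- "All subjects enrolled in the study should retain various original data and documents, both for retention and for intentional analysis (ITT Analysis").

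The same section then lists reasons for removing subjects, among them "Failing to obtain observation data". It adds that a case with unavailable data should be regarded as outside the analysis set, after joint discussion.

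The follow-up that all subjects are meant to have is set elsewhere. Section 5(5) states: "Adverse events and severe adverse events are assessed separately in 30 ± 5 days after surgery". Section 7.5 states: "Each subject is observed up to 30 days after surgery, and efficacy and safety are evaluated at the end of the follow-up". Section 8.2(2) bases the CCI on all complications and adverse events after surgery and names no end date.

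**The concern.** In a trial of continuing treatment, an AE may be a reason to stop the treatment, and the plan must then say whether observation goes on. Here the intervention is one operation. Once it is over there is nothing left to stop, so an operated subject who leaves under ground (2) or (3) can only be leaving observation. A complication or a device defect is not in itself a reason to stop recording outcomes. In a device safety trial these are the events under study.

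What is at stake is the 30-day AE/SAE assessment and the part of the CCI that depends on complications arising after the subject leaves. Subjects without problems would be followed in full, while some with problems would not. Missing data tied to the outcome in this way understate complications, and an SAE may be left with no recorded outcome. An analysis plan cannot recover data that sites were never told to collect, so this belongs in the protocol.

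**Working it through.** The protocol gives no figure to reproduce on this point: no event rate, no drop-out rate, and no basis for the 168 subjects. The check is a reading of the sections against each other, followed by arithmetic on 84 per arm (section 7.6).

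**Reading the sections together, for a subject already operated on**

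1. Section 7.5 and section 5(5) set observation to 30 days, with AE/SAE assessment at 30 ± 5 days.
2. Section 7.7 defines a drop-out as someone who does not reach the end of that observation, and accepts grounds (2) and (3) as usual reasons.
3. After drop-out, the triggering AE is captured through CRF entry and sponsor notification, and data already collected are kept. The CRF sentence names drop-outs due to adverse events; it does not mention those due to a device defect.
4. The purpose given for contact is the reason for leaving. No sentence asks for the outcome of the event, later complications, or the 30 ± 5 day assessment.
5. Missing observation data are a removal criterion. Section 7.7 therefore pulls two ways: data are retained for ITT, yet a subject whose data could not be obtained may be left out.

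**Uncertainty from each lost outcome**

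For an arm of n = 84 with k unknown 30-day outcomes, counting all k as event-free and then all k as events gives a range of width k/84:

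- k = 1: 1/84 = 1.2 percentage points
- k = 2: 2/84 = 2.4 points
- k = 4: 4/84 = 4.8 points
- k = 8: 8/84 = 9.5 points

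The value of k is not known. These are illustrations.

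**Understatement if the lost subjects are also left out**

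If e of 84 subjects have an event and m of those e are lost and excluded, the observed rate is (e − m)/(84 − m). Both e and m are assumptions:

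| e | True rate | m | Observed rate |
|---|---|---|---|
| 4 | 4/84 = 4.8% | 1 | 3/83 = 3.6% |
| 4 | 4.8% | 3 | 1/81 = 1.2% |
| 8 | 8/84 = 9.5% | 2 | 6/82 = 7.3% |
| 8 | 9.5% | 4 | 4/80 = 5.0% |
| 8 | 9.5% | 6 | 2/78 = 2.6% |
| 17 | 17/84 = 20.2% | 4 | 13/80 = 16.3% |
| 17 | 20.2% | 13 | 4/71 = 5.6% |

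This table is an upper view. It assumes that the triggering event is not counted, which the CRF and ITT rules should prevent if they are followed. If the subject is kept with the first event recorded, the loss is confined to later complications and to the outcome of that event.

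**The case against.** The strongest reply is that section 7.7 describes drop-out and does not order it. Ground (2) covers only events that prevent participation, so an AE or device defect is not a ground in itself. No sentence tells a site to stop observing anyone. Sections 5(5) and 7.5 apply to each subject, and section 5(6) places the analysis after all subjects' follow-up. Ground (2) also has a proper use before surgery: section 7.3 allows up to 14 days between consent and enrolment, and both systems are examined before use (section 5(3)), so an early AE or a defect found at that check could prevent the operation.

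Most of this stands, and it limits the point. The loss follows from the definition of drop-out together with silence on what to collect afterwards. It does not follow from an instruction. The fix must leave the pre-operative use alone. But the general 30-day rule does not close the gap, because section 7.7 is where the protocol says what happens when that rule is not met, and there it asks only for the reason.

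A reader might infer more than the documents support:

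- *The site only asks the reason.* It must also make the CRF entry, notify the sponsor and retain data for ITT.
- *The test product will look safer than the control.* Section 7.7 applies to both arms. A bias between arms needs unequal loss, and nothing shows that.
- *A malfunction is both a primary failure and a reason to stop observing.* Section 8.1 counts a conversion forced by malfunction as a failure but does not say that converted subjects drop out. Surgical success is settled during the operation, so later loss of follow-up does not affect it.
- *All 30 days are lost, in most of the subjects who drive the CCI.* Leaving on day 0 to 3 would forgo 30 − 3 = 27 to 30 − 0 = 30 days, but only if observation stopped at once, which no sentence says. The number of such subjects cannot be derived from the protocol.

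The listed safety indicators are also largely intraoperative or in-hospital. Section 9.1(2) counts AE incidence only to discharge. That narrows the exposure to the 30-day assessment and later complications. It also shows that the discharge window and the 30-day window have to be reconciled.

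**Conclusion.** The point holds in limited form. For operated subjects, section 7.7 allows observation to end because of an AE, SAE, device defect or investigator decision, and requires neither the 30 ± 5 day assessment nor the later complications needed for the CCI. Its removal criterion for missing data can compound the loss. The 30-day safety outcome can therefore be missing selectively in subjects with events, which would understate complications in whichever arm it occurs.

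The size is 1.2 percentage points of best-to-worst-case range per lost outcome in an arm of 84. The total is unknown. The conclusion assumes that sites apply section 7.7 as written and do not complete the 30-day assessment on their own initiative. This is worth correcting before the trial relies on its 30-day data, but it does not threaten the primary comparison.

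**What to change.** In section 7.7:

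1. Limit grounds (2) and (3) to subjects who have not yet been operated on.
2. State that an operated subject who has an AE, SAE, device defect or conversion stays under observation and has the 30 ± 5 day AE/SAE and complication (CCI) assessment, by telephone if needed. Only withdrawal of consent to follow-up ends observation.
3. Use the contact routes already listed to collect the outcome of the event as well as the reason for leaving.

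At the same time, reconcile the AE window in section 9.1(2) with the 30 days in sections 5(5) and 7.5.

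The cost is a change of wording and some extra follow-up calls, using contact that section 7.7 already requires. A few more late complications may be recorded, in either arm.

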8.1 Primary outcome measure: surgical success rate

The surgical success rate is defined as the proportion of successfully operative subjects in the experimental group or the control group.

Surgery conversion in this study means a robotic surgery has to be converted to a

laparoscopic surgery. Usually there are 3 kinds of reasons: active conversion, passive conversion and malfunction of the endoscopic instrument control system.

(1) Active conversion:

During the surgery, surgeons may encounter some situations that make them impossible to keep the operation going such as severe adhesion, anatomical variation or failing to expose the surgical site. Or when surgeons are dissociating the tissue, they have difficulties to find certain important vascular structure and to make a normal anatomy of the clearance. At this point, surgeons initiatively decide to convert to a laparoscopic surgery.

(2) Passive conversion:

During the surgery, some unexpected accidents happen and surgeons have to convert to laparoscopic surgery. Usually these accidents include injury of tissues and organs, unstoppable bleeding, and difficult suture using the surgical robot. Passive conversion is related to surgical techniques of the surgeons. With the experience accumulating and the operative skill improving of surgeons, the passive conversion rate will decrease significantly.

(3) Malfunction of the endoscopic instrument control system:

Serious malfunction of the test product may occur during the surgery (such as strong interference between the console and the operative part, the operative arm dysfunction and can't be repaired by resetting, surgical instrument can't loosen the tissue, etc.) The operation is unable to continue, so surgeons have to convert to laparoscopic surgery. Usually the malfunction is caused by unreasonable design, unqualified instruments or inappropriate operation of the product arms. It indicates the deficiency of the test product.

Notes:

1) Surgical success is defined as the successful completion of all surgical operations through the experimental products or the control products.

2) Surgical failure is defined as the unaccomplishable surgical operations using the experimental or control products as planned. The reason includes passive conversion and malfunction of the products. Noticeably, active conversion does not mean a surgical failure.

8.2 Secondary outcome measures:

(1) The breakage rate of gallbladder:

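### Section 7.7 keeps all enrolled subjects for ITT, then removes randomised subjects from the analysis set on grounds that can emerge after the surgical outcome is known

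*Protocol*

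**What the plan says.** Section 7.7 of the protocol makes three statements about who is analysed.

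- On retention: "All subjects enrolled in the study should retain various original data and documents, both for retention and for intentional analysis (ITT Analysis").
- On removal: subjects meeting any of four criteria are to be removed. Criterion (1) is "Those found to violate the inclusion criteria or meet the exclusion criteria during the trial". Criteria (2) and (3) concern consent. Criterion (4) is failure to obtain observation data, without saying which data.
- On the effect of removal: it helps to determine the endpoint data set. The wording that keeps a case out of the analysis set is: "condition that affects the treatment or safety evaluation of the case, such as unavailable observational data, the case should be considered as not included". On who takes this decision, the section adds: "It must be decided after discussion between the principal investigator, the data manager, the statistical analyst and the sponsor".

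Four other sections bear on this.

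- Section 8.1, note 2, on failure: "The reason includes passive conversion and malfunction of the products. Noticeably, active conversion does not mean a surgical failure".
- Section 7.5: "Each subject is observed up to 30 days after surgery, and efficacy and safety are evaluated at the end of the follow-up".
- Section 7.2, exclusion (12), is open-ended: "Other situations that researchers consider it inappropriate to participate in this clinical trial".
- Section 2: "This clinical trial is a prospective, multicenter, randomized, single-blind, parallel-controlled study".

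**The concern.** A set cannot both hold all enrolled subjects and leave out those who meet the removal criteria. Section 7.7 does not say that two sets are meant, or which one carries the primary comparison. Two analysts could follow it faithfully and build different primary sets from the same data.

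The timing makes this more than untidy. Surgical success is settled on the operating table, while the period in which an eligibility breach may be found runs to day 30. A subject can therefore be taken out after the result is known. The trial aims to show non-inferiority with 84 subjects per arm. If failures are few, the conclusion may turn on one or two of them.

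**Working it through.** **Can a recorded failure leave the set?**

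1. Most eligibility is settled beforehand by the ultrasound and laboratory tests of section 10.1. Some exclusions may still be first confirmed at operation: gangrene or perforation (exclusion 7) and cancer (exclusion 9). Exclusion (12) rests on judgement.
2. Under 8.1 only passive conversions and malfunctions are failures. Removing an active conversion takes no failure out. Removing a passive conversion in, say, a perforated gallbladder does.
3. Criterion (4) is not tied to the primary outcome. Read broadly, it could remove a subject whose failure was recorded at surgery but whose later data are missing. A drop-out for a device defect reaches exclusion only by this indirect route or through the clause on affected evaluations.
4. The operating surgeon uses the robot and scores it afterwards (8.2, item 7), so cannot be blind to arm. The deciding group includes the principal investigator and the sponsor. Section 7.7 does not ask that they decide without sight of arm and outcome.

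**How much could it matter?**

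The one figure available is 84 per arm (section 7.6; 84 + 84 = 168). Failure counts and margins below are assumptions, because the protocol states neither.

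For a success proportion p = x/n and z = 1.96, the Wilson limits l and u are

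[p + z²/(2n) ± z√(p(1−p)/n + z²/(4n²))] / (1 + z²/n).

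The Newcombe lower limit for test (T) minus control (C) is

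L = (pT − pC) − √[(pT − lT)² + (uC − pC)²].

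Example with 4 v 1 failures:

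- All kept: pT = 80/84 = 0.9524, lT = 0.8839; pC = 83/84 = 0.9881, uC = 0.9979. L = −0.0357 − √(0.0685² + 0.0098²) = −0.1049.
- One test failure removed: pT = 80/83 = 0.9639, lT = 0.8990. L = −0.0242 − √(0.0649² + 0.0098²) = −0.0898.

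Lower two-sided 95% limits in percentage points, with Miettinen-Nurminen (MN) as a check:

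| Assumed failures, test v control | Removed | Success, test v control | Newcombe | MN |
|---|---|---|---|---|
| 4 v 1 | none | 80/84 v 83/84 | -10.49 | -10.61 |
| 4 v 1 | 1 test failure | 80/83 v 83/84 | -8.98 | -9.08 |
| 5 v 1 | none | 79/84 v 83/84 | -12.06 | -12.19 |
| 5 v 1 | 2 test failures | 79/82 v 83/84 | -9.10 | -9.20 |
| 5 v 1 | 1 failure per arm | 79/83 v 83/83 | -11.75 | -11.77 |
| 5 v 0 | none | 79/84 v 84/84 | -13.19 | -13.22 |
| 5 v 0 | 2 test failures | 79/82 v 84/84 | -10.21 | -10.24 |
| 5 v 0 | 3 test failures | 79/81 v 84/84 | -8.56 | -8.59 |
| 5 v 0 | all 5 test failures | 79/79 v 84/84 | -4.64 | -4.66 |
| 5 v 0 | 3 successes per arm | 76/81 v 81/81 | -13.65 | -13.68 |
| 3 v 0 | none | 81/84 v 84/84 | -9.98 | -10.01 |
| 7 v 1 | none | 77/84 v 83/84 | -15.09 | -15.22 |
| 7 v 1 | 1 test failure | 77/83 v 83/84 | -13.76 | -13.89 |

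Reading the table by assumed margin:

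- **10 points:** one removal reverses the conclusion at 4 v 1, two at 5 v 1, three at 5 v 0.
- **15 points:** a single removal matters only with more failures, as at 7 v 1.
- **5 points:** 5 v 0 needs all five failures removed.
- **Direction:** one failure out of each arm at 5 v 1 leaves the limit beyond 10 points. Dropping three successes per arm at 5 v 0 moves it against the claim.

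**The case against.** The strongest reply is that the contradiction is inferred. Section 7.7 never says that the ITT data and the analysis set are the same set. One can read it as full data kept for ITT plus a second, cleaned set, with the SAP naming the primary one. The SAP is not at hand and may do so. That reading is open, but the text does not state it. The removal rule is mandatory and has no limit of set or time, so an SAP that confined it to a per-protocol set would be narrowing 7.7, not applying it.

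The route is also narrow. Screening comes before surgery, and severe adhesion or failed exposure counts as active conversion, so many difficult cases would not be failures. Malfunctions are not eligibility breaches. Missing later data need not make a recorded conversion unavailable. The data manager and statistician sit in the deciding group, and the operating surgeon is not named in it. All this stands as a limit on how often a failure would be lost. It does not close the route.

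The figures depend on assumed counts, margin and method. With a Wald limit, (pT − pC) − 1.96√[pT(1−pT)/nT + pC(1−pC)/nC], 4 v 1 with all kept gives −8.7, already inside 10 points. The case of 3 v 0 sits on the line: −9.98 by Newcombe, −10.01 by MN. That changes which counts flip, not whether removals can decide the result. By Wald, 5 v 1 is −10.3 with all kept.

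**Conclusion.** The concern holds and should be fixed. As written, 7.7 allows a randomised subject to leave the analysis set after the primary outcome is known, by a decision not required to be blind to arm or outcome, and it conflicts with the section's own ITT sentence. This is a stated rule, not a detail left to the SAP.

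In the worked cases that remove only test-arm failures, each removal moves the Newcombe lower limit towards the claim by about 1.3 to 2 points (for example −10.49 to −8.98 for one, −13.19 to −4.64 for five). Whether that changes the conclusion depends on the true counts and margin, which the protocol does not give. The direction of bias depends on whom the removals fall on. The ambiguity about the primary set does not depend on any of these assumptions.

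**What to change.** Reword 7.7 as follows.

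- **Primary (ITT) set:** every randomised subject with valid consent, in the assigned arm. Eligibility breaches found after randomisation stay in.
- **Outcome:** score what was observed at surgery whatever drop-out follows, using data after withdrawal of consent only as the consent allows. Malfunction and passive conversion remain failures, as 8.1 has it.
- **Randomised but not operated on:** keep in the set, list by arm with the reason, and treat the outcome as missing. The method may go in the SAP.
- **Per-protocol set:** name it, and apply criteria (1) and (4) and the clause on affected evaluations only there. Fix its membership by review without sight of arm or outcome.
- **Reporting:** give the non-inferiority comparison in both sets.

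The cost is wording in one section, with no extra patients or procedures and no change to a clinical rule. The drawback is that a few ineligible cases stay in the primary set, which is why both sets are reported.
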